### **7.3 TREATMENT COMPLIANCE**

Not applicable.

**7.4 PRIMARY ENDPOINT(S)**

[figure not shown]
Only descriptive statistics are planned to be performed in the overall sample as well in the stratified by time of diagnosis subgroups.

**7.5 SECONDARY ENDPOINT(S)****7.5.1 Key secondary endpoint(s)**

This section is not applicable as no key secondary endpoint has been specified in the protocol.

**7.5.2 (Other) Secondary endpoint(s)**

Only descriptive statistics are planned to be performed.

**7.7 EXTENT OF EXPOSURE**

This section is not applicable as this is an observational trial with no study treatment administration.

**7.8 SAFETY ANALYSIS****7.8.1 Adverse events**

Safety analysis will be performed in the FAS population. No stratified analysis for safety will be considered. All adverse events will be coded according to MedDRA dictionary.

The analyses of adverse events (AEs) will be descriptive in nature. All analyses of AEs will be based on the number of subjects with AEs and NOT on the number of AEs.

The frequency of subjects with adverse events following the ICF signature will be summarized according to primary system organ class and preferred term (MedDRA version to be displayed in the tables). System organ classes will be sorted alphabetically, preferred terms will be sorted by frequency (within system organ class).

Summary statistics will be provided for the following categories: all AEs, all SAEs and AEs with causal relationship to BI medication. AE listings will also be provided.

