## **9.5 DATA SOURCES**

The study will mainly include the recording of new data through a web based system for data collection. Data will be collected by the study doctors as they occur according to standard clinical practice in the approximate visiting schedule indicated above.

Source (primary) patient data related to their medical and IPF history will be collected by the investigators from the patient's medical files/records and will be documented in the relevant eCRF section.

Data regarding treatment modifications, concomitant treatments, study related routine clinical assessments, adverse events (ADRs) and survival status will also be collected. If a patient withdraws early from the study, they will be contacted via telephone at the end of the Study in order to evaluate their survival status. Another follow-up assessment should be performed if possible (unless reason for discontinuation is erroneous enrolment of the patient into the study at baseline), and data should be entered on the eCRF of the next planned visit unless the patient has actively withdrawn consent for any kind of future contacts.

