### Collection of AEs

The study design is of non-interventional nature and the study is conducted within the conditions of the approved marketing authorisation. Sufficient data from controlled interventional trials are available to support the evidence on the safety and efficacy of Nintedanib. For this reason the following AE collection and reporting requirements have been defined.

The following must be collected by the investigator in the (e)CRF from signing the informed consent onwards until the end of the study:

- all ADRs related to Nintedanib, taken for idiopathic pulmonary fibrosis (serious and non-serious),
- all AEs with fatal outcome in patients exposed to Nintedanib, taken for idiopathic pulmonary fibrosis

All ADRs, including those persisting after study completion must be followed up until they are resolved, have been sufficiently characterized, or no further information can be obtained.

The investigator carefully assesses whether an AE constitutes an ADR using the information below.

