#### Expedited Reporting of AEs and Drug Exposure During Pregnancy

The following must be reported by the investigator on the NIS AE form from signing the informed consent onwards until the end of the study to the [REDACTED] at [REDACTED]

Type of Report	Timeline
All serious ADRs associated with Nintedanib, taken for idiopathic pulmonary fibrosis	immediately within 24 hours
All AEs with fatal outcome in patients exposed to Nintedanib, taken for idiopathic pulmonary fibrosis	immediately within 24 hours
All non-serious ADRs associated with Nintedanib, taken for idiopathic pulmonary fibrosis	7 calendar days
All pregnancy monitoring forms	7 calendar days

The same timelines apply if follow-up information becomes available for the respective events. In specific occasions the Investigator could inform the Sponsor upfront via telephone. This does not replace the requirement to complete and fax the NIS AE form.

Information required

For each reportable adverse event, the investigator should provide the information requested on the appropriate (e)CRF pages and the NIS AE form. The NIS AE form and Pregnancy Monitoring Forms should be submitted to the [REDACTED] at [REDACTED]. [REDACTED] For details regarding Pregnancy Monitoring Forms, please refer to [Section 11.2](#), paragraphs entitled, “Pregnancy” and “Expedited Reporting of AEs and Drug Exposure During Pregnancy.”

Reporting of related Adverse Events associated with any other BI drug

The investigator is encouraged to report all adverse events related to any BI drug other than Nintedanib taken for IPF, according to the local regulatory requirements for spontaneous AE reporting at the investigator’s discretion by using the locally established routes and AE report forms. The term AE includes drug exposure during pregnancy, and, regardless of whether an AE occurred or not, any abuse, off-label use, misuse, medication error, occupational exposure, lack of effect, and unexpected benefit.

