### **6.3 SUBJECT SETS ANALYSED**

The statistical analysis of the study will be based on the Full Analysis Set (FAS).

FAS is comprised of all subjects enrolled in the study with at least one measurement of the primary endpoint during the trial. This population will be used to run any statistics of the study. As there is no BI medication or product given for this study, there is not going to be any Treated Set. Therefore, any safety analysis will be performed also in the FAS.

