## **7. PLANNED ANALYSIS**

Continuous variables will be listed as mean value with standard deviation (SD) and median, along with minimum and maximum values (depending on the underlying distribution). The minimum and maximum values will have the precision of the data reported; mean, median values will have one additional decimal, whereas SD will have two additional decimals.

Categorical values will be listed as absolute and relative frequencies. Tabulations of frequencies for categorical data will include all possible categories and will display the number of observations in a category as well as the percentage (%) relative to the respective group (unless otherwise specified, all subjects in the respective subject set whether they have non-missing values or not). The precision for percentages should be one decimal point, unless the denominator is smaller than 100 (in all treatment columns), in which case percentages are given in integer numbers.

As soon as all patients are recruited and have the baseline visit recorded, then this visit will be analyzed. The information to be reported is shown at the corresponding revised display plan of the study, dated 24 April 2020.

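### AE percentages are computed over all FAS patients, although the protocol requires only nintedanib reactions and fatal AEs in nintedanib-exposed patients to be collected

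*SAP*

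**What the plan says.** **Collection.** Protocol section 11.2 (Collection of AEs) names two items that must go into the eCRF from consent to end of study: "all ADRs related to Nintedanib, taken for idiopathic pulmonary fibrosis (serious and non-serious", and "all AEs with fatal outcome in patients exposed to Nintedanib, taken for idiopathic pulmonary fibrosis". Section 9.5 is in line with this narrow scope: "adverse events (ADRs) and survival status will also be collected". For the sponsor's other products, section 11.2 leaves matters to spontaneous reporting: "The investigator is encouraged to report all adverse events related to any BI drug other than Nintedanib taken for IPF". All other AEs are kept in the site's patient files.

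**Analysis.** SAP section 6.3 reasons: "As there is no BI medication or product given for this study, there is not going to be any Treated Set". It concludes: "Therefore, any safety analysis will be performed also in the FAS". The FAS is every enrolled patient with at least one primary endpoint measurement, with no condition on the drug taken. Unless otherwise specified, SAP section 7 takes percentages over "all subjects in the respective subject set whether they have non-missing values or not". SAP section 7.8.1 applies this to three categories (all AEs, all SAEs, and AEs causally related to BI medication) and states: "Safety analysis will be performed in the FAS population. No stratified analysis for safety will be considered".

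**The concern.** The numerator and the denominator refer to different people. Events have to be collected only in connection with nintedanib, yet the base includes patients on pirfenidone, on other drugs or on no antifibrotic. SAP section 6.3 drops an exposed set because the study supplies no BI product. That is true, but it does not settle the matter: nintedanib is the sponsor's own drug, taken in routine care, and it is the one drug whose reactions must be recorded.

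The report would print low percentages under labels that suggest complete ascertainment in all patients. Protocol section 12 says the final report may be used for regulatory purposes and as a basis for publications, so these figures could be read as the frequency of AEs in Greek IPF patients or of reactions to nintedanib. They would be neither.

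**Working it through.** **1. Inputs.**
- Planned N: about 300 (protocol section 9.6). The primary endpoints in SAP section 5.1 include demographics and baseline items, so the FAS is in effect everyone enrolled.
- Denominator: the FAS (SAP sections 6.3, 7 and 7.8.1).
- Exposed share *s* and frequency among exposed patients *r*: neither is in the documents. All values below are assumptions.

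**2. The plan's own figure.** Protocol Table 2 gives an exact 95% interval of 6.85% to 13.97% for 10% of 300. Clopper-Pearson for 30/300 reproduces it, as it does every exact interval in the table. Table 2 is not in dispute; it serves as a reference below.

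**3. What has to be collected, and in whom** (protocol section 11.2).

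| Event after consent | Nintedanib-exposed | Never exposed |
|---|---|---|
| Reaction to nintedanib | required | cannot arise |
| Fatal AE | required | not required |
| Non-fatal AE unrelated to nintedanib, serious or not | not required | not required |

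The right-hand column contains no required event. The last row shows that *all AEs* and *all SAEs* are incomplete even among exposed patients, so a new denominator alone does not make those labels true.

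**4. Dilution.** If *u* is the frequency of voluntarily entered events in never-exposed patients,

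printed percentage = *s* × *r* + (1 − *s*) × *u*.

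If only required events are entered, *u* = 0, the printed figure is *s* × *r*, and the frequency among exposed patients is divided by 1/*s*, whatever *r* is.

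| Assumed uptake *s* | Exposed of 300 | Factor 1/*s* | Printed if *r* = 20% | Printed if *r* = 60% |
|---|---|---|---|---|
| 25% | 75 | 4.0 | 15/300 = 5% | 45/300 = 15% |
| 50% | 150 | 2.0 | 30/300 = 10% | 90/300 = 30% |
| 75% | 225 | 1.33 | 45/300 = 15% | 135/300 = 45% |
| 100% | 300 | 1.0 | 60/300 = 20% | 180/300 = 60% |

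**5. Same patients, two denominators.** With 50% uptake, 30 patients with an event are 10% of 300 (6.85% to 13.97%) but 20% of 150 exposed (13.9% to 27.3%). Ninety patients are 30.0% of 300 (24.9% to 35.5%) but 60.0% of 150 (51.7% to 67.9%). SAP section 7.8.1 plans no intervals for AEs; they are shown only to gauge the gap.

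**6. Does another SAP rule repair this?** SAP section 6.6 removes unknown data from denominators. Nothing there treats an empty AE record in a never-exposed patient as unknown, and SAP section 7 keeps patients in the base whether or not values are missing. The printed percentage is unchanged.

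**7. Who counts as exposed.** Protocol section 11.2 requires fatal AEs in patients exposed to nintedanib without saying when exposure must have occurred. A patient who stopped before consent and died after it falls within that wording, so the exposed set has to include use before consent.

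**The case against.** **The consequence is limited.** The study is not a PASS, nintedanib safety is not an objective, and treatments are not compared. The protocol narrows AE collection because it regards existing trial evidence on nintedanib as sufficient. Deaths, hospitalisations, infarctions, haemorrhage and perforation are followed as Annex 3 outcomes without restriction to nintedanib users, so the AE tables are not the main source on serious events. All of this stands and keeps the point below the primary analysis.

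**A careful reader could recover the frequency.** SAP section 5.2.2 summarises nintedanib use and section 7.8.1 adds AE listings. Rescaling works only for someone who knows the collection rule, which the SAP does not state, and the diluted figure is still the one printed.

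**Dilution is conditional.** The eCRF is not visible, and protocol section 9.3.2 has withdrawing patients asked about adverse events whatever drug they take. If extra events are entered, *u* exceeds zero and the exact factor no longer applies. The table would then mix required and voluntary reports, which is no easier to interpret.

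**A crude percentage ignores time on drug.** Protocol section 9.8.1 calls for incidence rates for events during follow-up. Changing the denominator does not supply person-time, and that limitation remains.

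**A stronger reading concerns strata.** A reader might infer that leaving safety unstratified is a concealed departure from the protocol. The documents do not support that. SAP section 7.8.1 says it openly. Protocol section 9.8.1 describes strata by time since diagnosis in general terms without naming adverse events, and the contents list shows a redacted entry after 9.8.1, so no duty to stratify AEs can be confirmed.

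**Conclusion.** The mismatch is in the text and should be corrected. As written, the SAP divides events that need be collected only in nintedanib-exposed patients by all FAS patients, and labels the result as all AEs and all SAEs. If only required events are entered, every such percentage understates the frequency among exposed patients by the factor 1/uptake, unless all FAS patients are exposed or no event occurs. The size cannot be fixed from the documents: 4.0, 2.0 or 1.33 at an assumed uptake of 25%, 50% or 75%. The labelling fault does not depend on uptake.

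No primary endpoint is affected. The absence of safety strata is not part of the finding; at most, a line in SAP section 4 could note it against the protocol's general stratification plan.

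**What to change.** **SAP section 6.3:** replace the closing sentence with a nintedanib-exposed subset of the FAS. It comprises patients with any recorded nintedanib use for IPF, before or after consent, up to end of study, derived from the start and stop dates that protocol section 9.4.4 requires. Show separately how many had use from consent onwards, since patients exposed only earlier have less opportunity for a recorded reaction.

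**SAP section 7.8.1:**
- Use this subset as the denominator of the AE tables, with its N in the column header.
- Rename the tables *nintedanib ADRs*, *serious nintedanib ADRs* and *fatal AEs in nintedanib-exposed patients*.
- Add a footnote stating what protocol section 11.2 required to be collected, and from when.
- List any other recorded events separately, without percentages.

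**Check:** confirm that the eCRF captures nintedanib dates. Protocol section 9.4.4 names the drug, but the concomitant medication list in Annex 4 does not.

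**Cost:** SAP wording, one derived flag and a footnote, with no new data collection if the eCRF follows section 9.4.4. The price is a smaller denominator. At an observed 20%, the exact 95% interval is 15.6% to 25.0% with 300 patients and 13.9% to 27.3% with 150.

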## **11.2 ADVERSE EVENT AND SERIOUS ADVERSE EVENT COLLECTION AND REPORTING**

The investigator shall maintain and keep detailed records of all AEs in their patient files.

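### The SAP's all-AE and all-SAE tables in the FAS claim more than the protocol requires sites to collect, and their base counts patients who cannot produce a required AE record

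*SAP*

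**What the plan says.** **Planned analysis.** SAP 7.8.1 counts subjects with events after consent, without stratification, and says: "Summary statistics will be provided for the following categories: all AEs, all SAEs and AEs with causal relationship to BI medication". On the analysis set, SAP 6.3 says: "Therefore, any safety analysis will be performed also in the FAS". Its reason is that the study supplies no BI product, so there is no treated set. The FAS takes every enrolled subject with at least one measurement of the primary endpoint, whatever the treatment. Unless otherwise specified, SAP 7 bases percentages on everyone in the set, with or without data.

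**Required collection.** Protocol 11.2 introduces its list with "The following must be collected by the investigator in the (e)CRF from signing the informed consent onwards until the end of the study". The list has two items. The first concerns suspected reactions to one drug: "all ADRs related to Nintedanib, taken for idiopathic pulmonary fibrosis (serious and non-serious". The second concerns deaths and depends on exposure to that drug, not on a causal judgement: "all AEs with fatal outcome in patients exposed to Nintedanib, taken for idiopathic pulmonary fibrosis".

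The expedited-reporting table in 11.2 has the same AE scope. The wider instruction in 11.2 concerns site files, not the eCRF: "The investigator shall maintain and keep detailed records of all AEs in their patient files". For other company drugs the wording is softer: "The investigator is encouraged to report all adverse events related to any BI drug other than Nintedanib taken for IPF", through spontaneous-reporting routes. Protocol 9.5 refers to "adverse events (ADRs) and survival status will also be collected".

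**The concern.** The two documents describe different data. A non-fatal AE not judged related to nintedanib has no required place in the eCRF. Nor does any AE in a patient never exposed to nintedanib for IPF. Rows labelled as all AEs and all SAEs would nevertheless be printed over the whole registry population.

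A reader could take them as the AE and SAE frequency of IPF patients in Greek expert centres, when they describe a subset collected for one drug over a mixed base. Protocol 12 foresees regulatory use and publications from the final report, so the tables may be read without the collection rule at hand.

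**Working it through.** **1. Figures in the documents.** Neither document gives an AE rate or a nintedanib share. The only computed figures are the precision intervals in Protocol Table 2. All 20 cells reproduce to two decimals by both methods. For n = 300 and 10%, the asymptotic interval is 0.10 ± 1.96 × √(0.10 × 0.90 / 300) = 6.61% to 13.39%, and the Clopper-Pearson interval is 6.85% to 13.97%, as stated. Nothing there is wrong; the point rests on comparing the texts.

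**2. Labels against required content.**

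| SAP 7.8.1 category | What the required eCRF data contain |
|---|---|
| All AEs | Nintedanib ADRs, plus fatal AEs in nintedanib-exposed patients |
| All SAEs | Serious nintedanib ADRs, plus the same fatal AEs |
| AEs related to BI medication | Nintedanib ADRs; a broad fit, but the label also covers other BI drugs, whose events go by discretionary spontaneous reports |

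**3. The base.** Nintedanib is not an entry condition: SAP 6.1 allows any standard-practice treatment, and Protocol 9.4.4 lists nintedanib among many drugs. A never-exposed patient cannot produce a required AE record but is counted in the FAS. SAP 6.6 leaves unknown data out of totals, but no section classes unexposed patients as unknown for AEs.

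**4. Effect on the percentage.** Let p be the proportion of exposed patients with an event and e the exposed share of the FAS. If only required events are entered:

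printed FAS percentage = (p × e × N) / N = p × e

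All inputs below are assumptions, for illustration only. N = 300, e = 50% (150 patients with nintedanib on or after consent), and intervals are Clopper-Pearson 95%. The middle row adds 30 assumed patients whose exposure ended before consent and who have no ADR.

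| Base | p = 30% | p = 10% |
|---|---|---|
| Exposed on or after consent | 45/150 = 30.0% (22.8–38.0) | 15/150 = 10.0% (5.7–16.0) |
| Past-only users added | 45/180 = 25.0% (18.9–32.0) | 15/180 = 8.3% (4.7–13.4) |
| FAS, as planned | 45/300 = 15.0% (11.2–19.6) | 15/300 = 5.0% (2.8–8.1) |

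At p = 30%, the printed value is 0.30 × 0.25 = 7.5% for e = 25% and 0.30 × 0.75 = 22.5% for e = 75%. The understatement relative to the exposed base is 1/e, or 4.0-, 2.0- and 1.33-fold at exposed shares of 25%, 50% and 75%.

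**5. Two gaps that affect any corrected base.** Protocol 11.2 does not say whether a patient who stopped nintedanib before consent counts as exposed. The medication list in Annex 4 omits nintedanib, although 9.4.4 lists it with start and stop dates.

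**The case against.** **The user count is already planned.** SAP 7.2 treats any treatment after enrolment as concomitant, and SAP 5.2.2 summarises nintedanib use with dosage and duration. A reader could roughly divide one table by the other, with help from the AE listings. This stands as partial recovery. It corrects neither the labels nor the printed base, and SAP 7.7 declares extent of exposure not applicable.

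**The collection rule is a minimum.** The CRF is not available here, so wider entry cannot be excluded. This stands, but voluntary entry would be incomplete and uneven, and would not justify an all-AE label either.

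**The protocol is less uniform than 11.2 alone suggests.** Section 9.5 speaks of ADRs without naming nintedanib, and 9.3.2 has withdrawing patients asked about adverse events. Section 9.5 is less specific than 11.2 but consistent with it; 9.3.2 sets no eCRF rule.

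**The SAP is to be read with the protocol.** SAP 3 assumes familiarity with it, so the label could mean all AEs collected. A table in a report does not carry that context unless it says so.

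**The FAS base is a defensible registry choice.** No treatment comparison is planned, and the FAS figure can be read as the share of registry patients with a reported nintedanib ADR. That reading is valid, but nothing in the planned labels conveys it. The absence of a study-supplied product does not resolve the problem, because AE collection is tied to nintedanib use in routine care.

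**The magnitude is assumed.** This is correct; the illustration shows the mechanism and does not estimate the distortion in this study.

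**Conclusion.** The concern holds. Followed as written, the SAP prints two mislabelled categories over a base that includes patients with no required AE record. This is a mismatch between analysis and collection, not merely missing detail, and the wording establishes it with high confidence.

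The numerical effect is unknown. It is the factor e, provided only required events reach the eCRF, and the documents do not give e. No primary result changes, because the registry is descriptive. The laboratory, vital-sign and Annex 3 outcome summaries are not affected: Annex 3 events are collected as study outcomes, and the SAP does not say that they feed the AE tables. The point should be fixed before the safety tables are produced.

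**What to change.** In SAP 6.3 and 7.8.1:

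- Relabel the categories as nintedanib ADRs, serious nintedanib ADRs, and fatal AEs in nintedanib-exposed patients.
- State the collection scope and the number exposed in each table.
- For the ADR tables, use as denominator the patients with any nintedanib for IPF on or after consent, derived from the start and stop dates in Protocol 9.4.4. Show patients whose exposure ended before consent, and any ADRs in them, separately.
- For fatal AEs, state whether past-only users count as exposed and use the matching base.
- List AEs entered beyond the required minimum separately. Keep the broader labels only if wider collection is documented.

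Reconcile Annex 4 with Protocol 9.4.4. Person-time rates are optional.

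The cost is SAP wording, relabelled tables and one exposure flag. The CRF must be checked first, above all for past nintedanib use, because of the Annex 4 omission. The statistical price is a smaller denominator and wider intervals: in the illustration, 22.8–38.0% for 45/150 against 11.2–19.6% for 45/300.
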